## Appendix 2. Meta-Analysis Tables, Listings, And Figures

Table Number	Title	Population	Topline
14.2.1	Sustained Pain Freedom from 2 to 24 Hours Post Dose: Secondary Analysis	mITT Subjects	
14.2.2	Sustained Pain Relief from 2 to 24 Hours Post Dose: Secondary Analysis	mITT Subjects	
14.2.3	Sustained Pain Freedom from 2 to 48 Hours Post Dose: Secondary Analysis	mITT Subjects	
14.2.4	Sustained Pain Relief from 2 to 48 Hours Post Dose: Secondary Analysis	mITT Subjects	
14.2.5	Pain Relapse from 2 to 48 Hours Post Dose: Secondary Analysis	mITT Subjects	

Figure Number	Title	Population	Topline
14.2.1	Forest Plot of Durability of Pain Relief	mITT Subjects	
14.2.2	Forest Plot of Durability of Pain Freedom	mITT Subjects	
14.2.3	Forest Plot of Probability of Pain Relapse	mITT Subjects	
14.3.1	Evaluation of Drug-Induced Hepatotoxicity (eDISH)	Treated Subjects	Y

### Appendix 3. Schedule of Assessments

Procedure	Screening Visit (3-28 days)	Baseline Visit (Randomization)	Onset of moderate or severe migraine	During Treatment 15, 30, 45, 60 and 90 minutes Post-Dose	During Treatment 2, 3, 4, 6, 8 hours Post-Dose	During Treatment 24 hours Post-Dose	During Treatment 48 hours Post-Dose	End of Treatment Visit
Eligibility Assessments								
Informed Consent	X							
Inclusion/Exclusion Criteria	X	X						
Medical History	X							
Prophylactic Migraine Medication/ Concomitant Medication 	X	X						X
Assessment of Migraine History (Signs and symptoms) paper source 	X							
Safety Assessments								
Physical Examination	X							X
Vital Signs/Physical Measurements 	X	X						X
Clinical Safety Laboratory Testing 	X							X

Procedure	Screening Visit (3-28 days)	Baseline Visit (Randomization)	Onset of moderate or severe migraine	During Treatment 15, 30, 45, 60 and 90 minutes Post-Dose	During Treatment 2, 3, 4, 6, 8 hours Post-Dose	During Treatment 24 hours Post-Dose	During Treatment 48 hours Post-Dose	End of Treatment Visit
ECG	X							X
Pregnancy Test 	X	X	X					X
Adverse Event and Serious Adverse Event Assessment 	X	X	X	X	X	X	X	X
Sheehan Suicidality Tracking Scale 	X	X						X
Clinical Drug Supplies/Study Supplies								
Randomize 		X						
Dispense Study Medication		X						
Administer 1 dose of study medication 			X					
Return unused study medication								X
eDiary returned/reviewed for completeness 								X
Efficacy Assessments								
Assessment of migraine pain 			X	X	X	X	X	

Procedure	Screening Visit (3-28 days)	Baseline Visit (Randomization)	Onset of moderate or severe migraine	During Treatment 15, 30, 45, 60 and 90 minutes Post-Dose	During Treatment 2, 3, 4, 6, 8 hours Post-Dose	During Treatment 24 hours Post-Dose	During Treatment 48 hours Post-Dose	End of Treatment Visit
Assessment of Migraine Symptoms (photophobia, phonophobia, and nausea - eDiary) 			X	X	X	X	X	
Functional Disability Scale 			X	X	X	X	X	
MQoLQ (Migraine Specified Quality of Life Questionnaire) 						X		
Preference of Medication 						X		

 Screening/Baseline Phase will be 3 - 28 days. The Baseline Visit may be scheduled but should only occur *after* all screening procedures are complete, patient meets inclusion/exclusion criteria, and lab test results have been received by the site.

 Patients will use eDiary to answer questions about their migraine symptoms upon experiencing a moderate/severe migraine headache. The patient will administer pre-dispensed study drug if 1) the headache remains moderate or severe; 2) the patient has completed all required migraine assessment questions in the eDiary, including their current most bothersome migraine symptom, and 3) the patient has not already taken prohibited medications (see protocol section 5.4).

 Patients should keep track of their concomitant medications throughout the study and report them to the study personnel at the End of Treatment Visit. Any medication taken for recurrent headache should be documented. Use of concomitant medications after randomization, including rescue medications, will be recorded by the patient on a paper diary and reported to the site.

 Height will only be captured at the Screening Visit. Weight body temperature, respiratory rate, blood pressure and heart rate will be collected at all time points where indicated. Sitting arterial systolic and diastolic blood pressure and pulse rate will be measured.

 All Screening Visit laboratory test results must be received prior to Baseline Visit.

 A serum pregnancy test will be completed at Screening and End of Treatment Visits as part of the standard laboratory tests (if appropriate). Confirmatory urine pregnancy test for WOCBP should be completed on site at Baseline Visit and any subsequent visits for confirmation at the Investigator's discretion. Home pregnancy test will be provided to WOCBP after completion of baseline visit.

 SAEs are reported from the time of informed consent and non-serious AEs are reported from baseline. All ongoing non-serious AEs and SAEs will be followed to resolution or until investigator deems there will be no further status change. SAE and AE's that occur during the treatment period should be reported to the site.

 This scale will be clinician administered, completed on site, and will be in paper. The source document will be provided by Biohaven. The assessment period for completing the scale will be 30 days prior to Screening, and since the last visit for the remainder of the study.

 Patients will be randomized in the IWRS system at the Baseline Visit (Randomization Day 01)

 Patient should be instructed that the dose should be taken once the migraine attack reaches moderate or severe pain.

 Site staff to review and confirm entries with patients and confirm all data points are transferred to the system and reset eDiary for future patient use, PRIOR to the patient leaving the clinic.

 ± Windows for timeframe around efficacy assessments (15, 30, 45, 60, 90 min, 2, 3, 4, 6, 8, 24 and 48 hours) will be automated and captured in the eDiary.

 These scales will be captured in the eDiary. Patients will also be asked about their most bothersome symptom at the time of reporting and treating a qualifying migraine.

 Paper source document will be used to capture Migraine History. Patients will also be asked about their typical most bothersome symptom when having a migraine.

## **Appendix 4. Supportive Analyses**

### **1 DURABILITY ENDPOINTS**

New durability endpoints were defined for pain freedom, pain relief, most bothersome symptom, functional disability, nausea, photophobia, and phonophobia. For each of these endpoints, durability was measured during six time periods:

- 2 to 24 hours
- 3 to 24 hours
- 4 to 24 hours
- 2 to 48 hours
- 3 to 48 hours
- 4 to 48 hours

For pain freedom and pain relief, the 2 to 24 hour and 2 to 48 hour durability endpoints were previously defined in the SAP in Sections [5.7.4.5](#)– [5.7.4.8](#).

Pain freedom, pain relief, most bothersome symptom, and functional disability were assessed using the mITT population. Nausea, photophobia, and phonophobia were assessed using mITT subjects who reported the given symptom as present at the start of their treated migraine.

For all ad-hoc durability endpoints, the following were presented:

- The number and percentage of subjects who are successful. These are presented by stratum and treatment group, with ASE and 95% asymptotic CIs.
- Common risk difference with sample size, p-value, ASE, and 95% asymptotic CIs.
- Risk difference within each strata with sample size, p-value, ASE and 95% asymptotic CIs.
- A plot of the risk differences within each strata, and common risk difference (similar to the risk difference plot produced by SAS Proc Freq).
- Common risk for each treatment with sample size, ASE, and 95% asymptotic CIs.

The “risk” is the probability of the given endpoint (success) through the given durability period.

## **1.1 Sustained Pain Freedom**

The ad-hoc sustained pain freedom endpoints were:

- Sustained Pain Freedom 3 to 24 hours
- Sustained Pain Freedom 4 to 24 hours
- Sustained Pain Freedom 3 to 48 hours
- Sustained Pain Freedom 4 to 48 hours

Sustained pain freedom for the above time periods were defined in a manner similar to that used for sustained pain freedom from 2 to 24 hours and 2 to 48 hours.

Sustained pain freedom was assessed using the number of mITT subjects who experienced no headache pain (response of 0 on the Likert scale) at all time points from the starting time point (3 or 4 hours post-dose) through the ending time point (24 or 48 hours post-dose). Subjects with missing pain scores at 1 or fewer time points, given that they had responses of no pain at all other time points including the starting and ending time points (and 24 hours for periods through 48 hours), were considered as successes. Subjects with missing data at greater than 1 post-dose time point, missing data at either the starting or ending time point (or 24 hours for periods through 48 hours), or with any pain score greater than 0 were considered as failures.

## **1.2 Sustained Pain Relief**

The ad-hoc sustained pain relief endpoints were:

- Sustained Pain Relief 3 to 24 hours
- Sustained Pain Relief 4 to 24 hours
- Sustained Pain Relief 3 to 48 hours
- Sustained Pain Relief 4 to 48 hours

Sustained pain relief for the above time periods were defined in a manner similar to that used previously for sustained pain relief from 2 to 24 hours and 2 to 48 hours.

Sustained pain relief was assessed using the number of mITT subjects who experienced no or mild headache pain (response of 0 or 1 on the Likert scale) at all time points from the starting time point (3 or 4 hours post-dose) through the ending time point (24 or 48 hours post-dose). Subjects with missing pain scores at 1 or fewer time points, given that they had responses of no or mild pain at all other time points including the starting and ending time points (and 24 hours for periods through 48 hours), were considered as successes. Subjects with missing data at greater than 1 post-dose time point, missing data at either the starting or ending time point (or 24 hours for periods through 48 hours), or with any pain score greater than 1 were considered as failures.

### **1.3 Sustained Freedom from Most Bothersome Symptom**

The ad-hoc sustained freedom from the MBS endpoints were:

- Sustained Freedom from MBS 2 to 24 hours
- Sustained Freedom from MBS 3 to 24 hours
- Sustained Freedom from MBS 4 to 24 hours
- Sustained Freedom from MBS 2 to 48 hours
- Sustained Freedom from MBS 3 to 48 hours
- Sustained Freedom from MBS 4 to 48 hours

Sustained freedom from MBS for these time periods is defined in a manner similar to that used for sustained pain freedom from 2 to 24 hours and 2 to 48 hours.

Sustained MBS freedom was assessed using the number of mITT subjects who did not have their MBS (response of absent) at all time points from the starting time point (2, 3 or 4 hours post-dose) through the ending time point (24 or 48 hours post-dose). Subjects with missing MBS scores at 1 or fewer time points, given that they had responses of absent MBS at all other time points including the starting and ending time points (and 24 hours for periods through 48 hours), were considered as successes. Subjects with missing data at greater than 1 post-dose time point, missing data at either the starting or ending time point (or 24 hours for periods through 48 hours), or with any MBS present at any time point in the period were considered as failures.

### **1.4 Sustained Freedom from Functional Disability**

The ad-hoc sustained freedom from functional disability endpoints were:

- Sustained Freedom from Functional Disability 2 to 24 hours
- Sustained Freedom from Functional Disability 3 to 24 hours

- Sustained Freedom from Functional Disability 4 to 24 hours
- Sustained Freedom from Functional Disability 2 to 48 hours
- Sustained Freedom from Functional Disability 3 to 48 hours
- Sustained Freedom from Functional Disability 4 to 48 hours

Sustained freedom from functional disability for these time periods is defined in a manner similar to that used for sustained pain freedom from 2 to 24 hours and 2 to 48 hours.

Sustained freedom from functional disability was assessed using the number of mITT subjects who experienced normal functioning at all time points from the starting time point (2, 3 or 4 hours post-dose) through the ending time point (24 or 48 hours post-dose). Subjects with missing disability scores at 1 or fewer time points, given that they have responses of no disability at all other time points including the starting and ending time points (and 24 hours for periods through 48 hours), were considered as successes. Subjects with missing data at greater than 1 post-dose time point, missing data at either the starting or ending time point (or 24 hours for periods through 48 hours), or with any reported disability in the time period were classified as failures.

### **1.5 Sustained Freedom from Nausea**

The ad-hoc sustained freedom from nausea endpoints were:

- Sustained Freedom from Nausea 2 to 24 hours
- Sustained Freedom from Nausea 3 to 24 hours
- Sustained Freedom from Nausea 4 to 24 hours
- Sustained Freedom from Nausea 2 to 48 hours
- Sustained Freedom from Nausea 3 to 48 hours
- Sustained Freedom from Nausea 4 to 48 hours

Sustained freedom from nausea for these time periods was defined in a manner similar to that used for sustained pain freedom from 2 to 24 hours and 2 to 48 hours. However, the analysis population was restricted to those subjects with nausea reported as present at the start of their treated migraine.

Sustained nausea freedom was assessed using the number of mITT subjects who had nausea present at baseline and did not report nausea (response of absent) at any time point from the starting time point (2, 3 or 4 hours post-dose) through the ending time point (24 or 48 hours post-dose). Subjects with missing nausea scores at 1 or fewer time points, given that they had responses of no nausea at all other time points including the starting and ending time points (and 24 hours for periods through 48 hours), were considered as successes. Subjects with missing data at greater than 1 post-dose time point, missing data at either the starting or ending time point (or 24 hours for periods through 48 hours), or with any nausea present at any time point in the period were considered as failures.

## **1.6 Sustained Freedom from Photophobia**

The ad-hoc sustained freedom from photophobia endpoints are:

- Sustained Freedom from Photophobia 2 to 24 hours
- Sustained Freedom from Photophobia 3 to 24 hours
- Sustained Freedom from Photophobia 4 to 24 hours
- Sustained Freedom from Photophobia 2 to 48 hours
- Sustained Freedom from Photophobia 3 to 48 hours
- Sustained Freedom from Photophobia 4 to 48 hours

Sustained freedom from photophobia for these time periods was defined in a manner similar to that used for sustained freedom from nausea. The analysis population was restricted to those mITT subjects with photophobia reported as present at the start of their treated migraine.

Sustained photophobia freedom was assessed using the number of mITT subjects who had photophobia present at baseline and that did not report photophobia (response of absent) at any time point from the starting time point (2, 3 or 4 hours post-dose) through the ending time point (24 or 48 hours post-dose). Subjects with missing photophobia scores at 1 or fewer time points, given that they had responses of no photophobia at all other time points including the starting and ending time points (and 24 hours for periods through 48 hours), were considered as successes. Subjects with missing data at greater than 1 post-dose time point, missing data at either the starting or ending time point (or 24 hours for periods through 48 hours), or with any photophobia present at any time point in the period were considered as failures.

## **1.7 Sustained Freedom from Phonophobia**

The ad-hoc sustained freedom from phonophobia endpoints are:

- Sustained Freedom from Phonophobia 2 to 24 hours
- Sustained Freedom from Phonophobia 3 to 24 hours
- Sustained Freedom from Phonophobia 4 to 24 hours
- Sustained Freedom from Phonophobia 2 to 48 hours
- Sustained Freedom from Phonophobia 3 to 48 hours
- Sustained Freedom from Phonophobia 4 to 48 hours

Sustained freedom from phonophobia for these time periods was defined in a manner similar to that used for sustained freedom from nausea. The analysis population was restricted to those mITT subjects with phonophobia reported as present at the start of their treated migraine.

Sustained phonophobia freedom was assessed using the number of mITT subjects who had phonophobia present at baseline and that did not report phonophobia (response of absent) at any time point from the starting time point (2, 3 or 4 hours post-dose) through the ending time point (24 or 48 hours post-dose). Subjects with missing phonophobia scores at 1 or fewer time points, given that they had responses of no phonophobia at all other time points including the starting and ending time points (and 24 hours for periods through 48 hours), were considered as successes. Subjects with missing data at greater than 1 post-dose time point, missing data at either the starting or ending time point (or 24 hours for periods through 48 hours), or with any phonophobia present at any time point in the period were considered as failures.

The durability endpoints (e.g., pain freedom from 2 to 24 hours) will be analyzed in a meta-analysis that uses the data from both BHV3000-301 and BHV3000-302. These endpoints will be tested in a fix sequence, in the order shown below, with each test conducted at a two-sided alpha level of 0.05.

1. Sustained Pain Freedom from 2 to 24 hours
2. Sustained Pain Relief from 2 to 24 hours
3. Sustained Pain Freedom from 2 to 48 hours
4. Sustained Pain Relief from 2 to 48 hours
5. Pain Relapse from 2 to 48 hours

## **1.8 Supportive Durability Endpoints Evaluated by Meta-Analysis**

For the durability endpoints, the meta-analysis will mirror the durability analyses described above, with the addition of strata to represent each study. The common risk difference is computed using CMH weights, stratified by the use of prophylactic migraine medication (yes or no) and study (BHV3000-301 or BHV3000-302). For each endpoint, the risk difference is tested at a two-sided alpha level of 0.05. If a stratum (prophylactic medication use: yes or no) has sparse data (less than 5 subjects) then the strata will be pooled.

For all ad-hoc durability endpoints, the following were presented:

- The number and percentage of subjects who are successful. These are presented by stratum and treatment group, with ASE and 95% asymptotic CIs.
- Common risk difference with sample size, p-value, ASE, and 95% asymptotic CIs.
- Risk difference within each strata with sample size, p-value, ASE and 95% asymptotic CIs.
- A plot of the risk differences within each strata, and common risk difference (similar to the risk difference plot produced by SAS Proc Freq).
- Common risk for each treatment with sample size, ASE, and 95% asymptotic CIs.
- The common risk difference, with ASE, is also computed separately for each of the two studies.

The “risk” is the probability of the given endpoint (success) through the given durability period.

## **2 TIME TO EVENT ANALYSES**

### **2.1 Time to Rescue Medication**

Kaplan-Meier plots were created for the time to first use of rescue medication. The K-M plot covered the 24 hour period after dosing. Subjects who did not take rescue medication within 24 hours of dosing were censored at 24 hours and 1 minute. Regardless of pain or MBS response, subjects were considered at risk until the first use of rescue medication, loss to follow-up (last contact date), or the end of the 24 hour period, whichever came first. The analysis population consisted of mITT subjects.

Two tables were created to support the plot. The first table presented the median time to rescue medication along with 95% CIs calculated using the method of Brookmeyer and Crowley and the log-rank p-value. The second table presented the number of subjects at risk, with an event, censored, and the survival probability estimate (with 95% CI) for each period by treatment group.

## **2.2 Time to First Report of Absence of Various Symptoms**

For each of the following variables, two sets of Kaplan-Meier plots and tables were created:

- Time to First Report of Absence of Most Bothersome Symptom
- Time to First Report of Absence of Nausea
- Time to First Report of Absence of Photophobia
- Time to First Report of Absence of Phonophobia
- Time to First Report of Return to Normal Functioning

The first set of plots and tables was similar to those created for the time to rescue medication (using actual time). For the second set of plots, nominal (planned time point) as opposed to actual time was used for clinical event times. Censoring was measured using actual time as in all previous plots.

For both sets of analyses, the analysis population for MBS and functional disability was the set of mITT subjects. The analysis population for nausea, phonophobia, and photophobia was the subset of mITT subjects that reported the symptom as present at the onset of their study migraine. The y-axis for all plots represents the probability of the occurrence of the event of interest, and therefore are increasing from left to right.

### **2.2.1 Kaplan-Meier Plots and Tables: Actual Time for Event of Interest**

The first set of K-M plots and tables were created using actual time of censoring and actual time for the clinical event of interest. Subjects were censored at the actual time of their first use of rescue medication or last reported data point if lost to follow-up. Subjects who did not have the clinical event of interest by 8 hours post dose were censored at 496 minutes (480 minutes + 15 minute window + 1 minute).

### **2.2.2 Kaplan-Meier Plots and Tables: Nominal Time for Event of Interest**

The second set of K-M plots and tables were created for the above variables with nominal time (planned time of collection, e.g., 2 hours, 3 hours, etc.) used for clinical events of interest and actual time used for censoring events. Subjects were censored at the actual time of their first use of rescue medication or last reported data point if lost to follow-up. Subjects who did not have the clinical event of interest by 8 hours post dose were censored at 496 minutes (480 minutes + 15 minute window + 1 minute).

### **2.3 Supportive Time to Event Endpoints Evaluated by Meta-Analysis**

For the time to event endpoints, the meta-analyses will mirror the time to event analyses described above. Data from BHV3000-301 and BHV3000-302 will be pooled prior to conducting the analyses.

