#### 6.3.1 *Liver Toxicity Evaluation*

Potential drug induced liver injury are those events meeting Hy's Law, defined as:

1. Aminotransferases (AT) ALT or AST elevation > 3 times the upper limit of normal (ULN);
2. Total bilirubin (TBL) > 2 times ULN, without initial findings of cholestasis (elevated serum alkaline phosphatase); and

3. No other immediately apparent possible causes of AT elevation and hyperbilirubinemia, included but not limited to: viral hepatitis, pre-existing chronic or acute liver disease, or the administration of other drug(s) known to be hepatotoxic.

Any potential drug-induced liver injuries (DILIs), meeting the above defined criteria, will be reported as SAEs and tabulated by treatment group. A listing will be prepared that shows the AT and TBL values for all subjects that experience either AT > 3 times the upper limit of normal or TBL > 2 times the upper limit of normal at any time during the study.

Additionally, a table will be created that summarizes the incidence (as the number of subjects experiencing the given measurement post-randomization) of the following:

- >3x, >5x, >10x, and >20x ULN elevations of AST, ALT, and either ALT or AST
- Any elevations of bilirubin >1x ULN and >2x ULN
- Any elevations of ALP > 1.5x ULN
- Elevation of AST or ALT (>3x ULN) accompanied by elevated bilirubin (>1.5x ULN and >2x ULN)
- Elevation of AST or ALT along with an on-study AE of nausea, vomiting, anorexia, abdominal pain, or fatigue

An evaluation of Drug-Induced Serious Hepatotoxicity (eDISH) plot will be created by plotting the maximum total bilirubin against maximum ALT and presenting these data points by treatment group for the current study and the BHV3000-301/302 meta-analysis. The maximum values for each subject during the study will be identified as the maximum values that occur post-baseline, but not necessarily concurrently. Maximum total bilirubin (presented as xULN) will be plotted on a log scale on the y-axis and maximum ALT (presented as xULN) will be plotted on a log scale on the x-axis. A horizontal reference line will be placed at 2x ULN for maximum total bilirubin and a vertical reference line will be placed at 3x ULN for maximum ALT. The lower left quadrant will be labeled “Normal Range”. The upper left quadrant will be labeled “Hyperbilirubinemia”. The lower right quadrant will be labeled “Temple’s Corollary”. The upper right quadrant will be labeled “Possible Hy’s Law Range”.

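### The pooled time-to-event comparison of 301 and 302 names no strata, while both other pooled treatment comparisons stratify by study and prophylactic medication

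*SAP*

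**What the plan says.** SAP Appendix 4, section 2.3 covers the pooled time-to-event endpoints in two sentences. It says that "the meta-analyses will mirror the time to event analyses described above", and that "Data from BHV3000-301 and BHV3000-302 will be pooled prior to conducting the analyses". No strata are mentioned.

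The analyses being mirrored start in Appendix 4, 2.1 (time to rescue medication). One of its two supporting tables gives medians with "95% CIs calculated using the method of Brookmeyer and Crowley and the log-rank p-value". It names no stratification factor and no alpha level. Section 2.2 extends the approach to absence of the most bothersome symptom, nausea, photophobia and phonophobia, and to return to normal functioning, by describing the outputs as similar to those for rescue medication. Appendix 6 lists 11 pooled median-time tables: one for rescue medication and two (actual and nominal time) for each of the other five endpoints.

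The pooled durability analyses are set up differently. Appendix 4, 1.8 mirrors the single-study durability analyses "with the addition of strata to represent each study", and SAP 5.7.5 uses the same strata. Both also ask for the common risk difference separately in each trial, which section 2.3 does not.

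SAP 2.2 gives 1:1 randomisation in 302, stratified by prophylactic medication, and SAP 5.2.4 says that most analyses use that stratification. The SAP's Summary of Changes calls the added appendices post-hoc supportive analyses.

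**The concern.** At each event, a log-rank test compares the arm of the subject with the event against the rimegepant share of everyone still at risk. If two trials are merged without strata, each risk set mixes subjects from both trials and from both prophylaxis groups, although allocation was made within them.

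When the trials run at different speeds, subjects from the faster trial leave the risk set earlier. The hazard ratio in the mixture then drifts towards 1. The variance also takes no credit for the balance that randomisation gives within strata. Both effects make the test less sensitive.

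At stake are the sensitivity of a set of supportive pooled p-values and their consistency with the durability results in the same appendix. Without by-study results, a reader of the pooled curve also cannot see whether the two trials agree.

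**Working it through.** **1. The pooled treatment comparisons side by side**

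| SAP section | Comparison | Strata named | By-study result requested |
|---|---|---|---|
| 5.7.5 | Durability, common risk difference | Study and prophylaxis | Yes |
| Appendix 4, 1.8 | Supportive durability, common risk difference | Study and prophylaxis | Yes |
| Appendix 4, 2.3 | Time to event, log-rank via 2.1 and 2.2 | None | No |

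For the pooled time-to-event analyses the documents give no event count, hazard ratio, power or sample size, so there is no figure of the plan's own to reproduce.

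**2. Is the test without strata valid?**

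For event i let g = 1 if the subject is on rimegepant, and let p be the rimegepant share of the risk set. Then U = Σ(g − p), V = Σ p(1 − p) and z = U/√V. Without strata, p comes from the merged data. With strata, p comes from the subject's own study-by-prophylaxis stratum, and U and V are added over the four strata.

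Under no treatment effect and 1:1 allocation in both trials, the expected share is 1/2 in every stratum at every time. It is therefore 1/2 in the merged data too, and U has mean zero either way. Event rates that differ between trials do not bias the test.

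**3. Size of the loss, set A**

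All inputs are assumptions:
- 1100 subjects per trial, 1:1 in both trials.
- 40% placebo rescue at 24 h off prophylaxis, so the hazard is −ln(0.60)/24 = 0.0213 per hour.
- 15% on prophylaxis, with hazard × 1.5.
- Treatment hazard ratio 0.82, censoring just after 24 h, two-sided 0.05.
- 3000 null runs and 2000 runs under the alternative.

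A between-trial hazard ratio r is split as 1/√r and √r. The placebo rescue rates off prophylaxis are then 1 − 0.6^(1/√r) and 1 − 0.6^(√r): 30% and 51% at r = 2, and 26% and 59% at r = 3.

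| r | Type I error, no strata | Type I error, stratified | Power, no strata | Power, stratified | Loss (points) |
|---|---|---|---|---|---|
| 1 | 0.050 | 0.051 | 0.826 | 0.824 | −0.2 |
| 1.5 | 0.042 | 0.046 | 0.830 | 0.836 | 0.6 |
| 2 | 0.051 | 0.054 | 0.834 | 0.846 | 1.2 |
| 3 | 0.039 | 0.055 | 0.806 | 0.842 | 3.6 |

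The simulation error is about √(0.05 × 0.95/3000) = 0.004 on a type I error and √(0.83 × 0.17/2000) = 0.008 on a power. The loss at r = 1.5 cannot be told from zero with confidence. The 0.039 at r = 3 is a real departure, on the conservative side.

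**4. Set B, other assumed inputs**

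540 per arm per trial, 40% placebo rescue at 24 h, no prophylaxis effect, treatment hazard ratio 0.85, 3000 runs.

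| r | Power, no strata | Power, stratified | Loss (points) |
|---|---|---|---|
| 1 | 63.5% | 63.4% | −0.1 |
| 1.25 | 63.5% | 63.9% | 0.4 |
| 1.5 | 63.5% | 64.1% | 0.6 |
| 2 | 62.8% | 64.9% | 2.1 |

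The type I error without strata ran from 0.025 to 0.057, with the low values at a four-fold between-trial ratio. The two sets agree: about 0 to 2 points up to a two-fold ratio, and no inflation of type I error.

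**The case against.** Much of the opposing case stands.

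- **The missing strata are an inference.** The SAP never calls the test unstratified; it says the data are pooled first and names no strata. The log-rank test is named once, for time to rescue medication, and reaches the other five endpoints only because their outputs are described as similar. This stands, and it is a reason to state the test outright.
- **The durability analyses are not the only pooled output.** The liver plot in SAP 6.3.1 is specified as "presenting these data points by treatment group for the current study and the BHV3000-301/302 meta-analysis", with no strata. It is descriptive and carries no test, so the contrast drawn here is limited to treatment comparisons.
- **Kaplan-Meier work elsewhere in the SAP names no strata either** (5.7.6.2 and 5.7.6.7). True, but those sections specify curves and medians without a between-group test, so they have no p-value to stratify.
- **Part of the by-study display exists.** Appendix 5 lists 302-only Kaplan-Meier tables and figures that match the pooled ones in Appendix 6. That covers 302. Section 2.3 asks for no 301 counterpart beside them.
- **No claim rests on these p-values.** They are post hoc, appear in neither the hierarchy of SAP 5.2.5 nor the sequence of 5.7.5, and err on the conservative side. This stands and sets the priority.

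A reader might go further and infer that merging the trials abandons the randomised comparison or confounds treatment with study. That would need unequal allocation in 301. The documents give 1:1 for 302, are silent on 301, and contain nothing that suggests a different ratio. A reader might also infer a large loss of power: set B shows 59.2% against 67.1% at a four-fold between-trial ratio. That scenario is extreme, and the documents give no between-trial event rates to support it.

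**Conclusion.** The inconsistency is real and minor. Within one appendix, the pooled time-to-event comparison ignores two factors that the pooled durability comparison uses, and no reason is given.

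The consequence is a small loss of sensitivity, without bias and without false-positive risk. This conclusion assumes 1:1 allocation in 301 as well as 302. The size also rests on the assumed rescue rate, treatment effect and between-trial ratio, since the documents supply none of these. The loss disappears if the two trials have the same event rates and grows only when they differ well beyond two-fold.

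The point ranks as a free improvement to a supportive analysis.

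**What to change.** 1. In Appendix 4, 2.3, specify a log-rank test stratified by study and prophylactic medication use. Both variables are already needed for 5.7.5 and 1.8, so this costs one added statement in the program. Say explicitly which of the six endpoints carry the test.
2. In the same section, request by-study curves, medians and test results beside the pooled ones, in line with the by-study risk differences in 1.8. The 302 outputs are already listed in Appendix 5.
3. For consistency, stratify the single-study log-rank test in 2.1, and wherever 2.2 carries it over, by prophylactic medication use. The cost is that these sections are written in the past tense, so an analysis described as done would be re-run. If it is, show both p-values and say why.

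If simple pooling is kept, section 2.3 should say so and give the reason.
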